5.3 Withdrawal of individual subjects

Subjects can leave the study at any time for any reason if they wish to do so without any consequences. The investigator can decide to withdraw a subject from the study for urgent medical reasons.

5.4 Replacement of individual subjects after withdrawal

Individual subjects will be replaced after withdrawal.

6. SAFETY REPORTING

6.1 Section 10 WMO event

In accordance to section 10, subsection 1, of the WMO, the investigator will inform the subjects and the reviewing accredited METC if anything occurs, on the basis of which it appears that the disadvantages of participation may be significantly greater than was foreseen in the research proposal. The study will be suspended pending further review by the accredited METC, except insofar as suspension would jeopardise the subjects' health. The investigator will take care that all subjects are kept informed.

6.2 AEs, SAEs and SUSARs

6.2.1 Adverse events (AEs)

Adverse events are defined as any undesirable experience occurring to a subject during the study, whether or not considered related to [the investigational product / the experimental intervention]. All adverse events reported spontaneously by the subject or observed by the investigator or his staff will be recorded.

6.2.2 Serious adverse events (SAEs)

A serious adverse event is any untoward medical occurrence or effect that at any dose:

- results in death;
- is life threatening (at the time of the event);
- requires hospitalisation or prolongation of existing inpatients' hospitalisation;
- results in persistent or significant disability or incapacity;
- is a congenital anomaly or birth defect;

- Any other important medical event that may not result in death, be life threatening, or require hospitalization, may be considered a serious adverse experience when, based upon appropriate medical judgement, the event may jeopardize the subject or may require an intervention to prevent one of the outcomes listed above.

The sponsor will report the SAEs through the web portal *ToetsingOnline* to the accredited METC that approved the protocol, within 15 days after the sponsor has first knowledge of the serious adverse events.

SAEs that result in death or are life threatening should be reported expedited. The expedited reporting will occur not later than 7 days after the responsible investigator has first knowledge of the adverse event. This is for a preliminary report with another 8 days for completion of the report.

6.3 Follow-up of adverse events

All AEs will be followed until they have abated, or until a stable situation has been reached. Depending on the event, follow up may require additional tests or medical procedures as indicated, and/or referral to the general physician or a medical specialist.

SAEs need to be reported till end of study within the Netherlands, as defined in the protocol

7. STATISTICAL ANALYSIS

7.1 Primary study parameter(s)

To assess the effect of feedback on external knee adduction moment (KAM) a linear mixed model and repeated measure analysis of variance will be used. Four outcomes parameters will be extracted from the gait cycle, i.e. the KAM peaks at early and late stance with the corresponding KFM values, the KAM during mid-stance, and the impulse (area under curve in %BW*H*sec) [13;43]. In Study A comparison will be made between baseline and gait modification conditions; in Study B the change over time will be calculated for both baseline and replication of learned pattern. The associations between the changes in KAM, KFM, kinematic pattern and pain will be determined.

To identify the factors which predict whether an individual is likely to achieve a good result using the bio-feedback training method, a linear mixed model will again be used.

Statistical significance will be accepted at p-values of less than 0.05. All analyses will be performed using SPSS software, version 21.0 (SPSS, Chicago, IL).

Changes in pain and function over time in study B, as reported using the WOMAC questionnaire and NRS pain scale will also be assessed using a linear mixed model. Patient reported pain and function will be compared during a no-treatment period (immediately following assessment for Study A) and also over time during the intervention period.

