Study design: Cross-sectional observational study (A) and uncontrolled experimental study (B). In the first study (A) a biofeedback algorithm using computer modelling will be tested on its feasibility in a cross-sectional observational study to establish measurement capability and quality in patient with OA of the knee (n=41). In a second study (B) an n uncontrolled trial will be carried out during 6 weeks to provide evidence for real-time feedback as an intervention in modifying gait in a subsample of the previous study (n=30¹). Follow-up measurements will be carried out 3 and 6 months after the end of the training. Modification of knee load and gait characteristics will be assessed by 3D motion analysis on the GRAIL (Gait real-time analysis interactive lab including an instrumented treadmill, a motion capture system and a semi cylindrical screen with virtual reality environment and real-time gait feedback).

Study population: 41 patients with medial knee osteoarthritis aged between 50 and 70.

Intervention (if applicable): Training protocol for gait modification once per week for 6 weeks, including feedback on the external knee adduction moment (KAM) and advice on home training.

Main study parameters/endpoints: Primary outcome measures are change in external knee adduction moment (KAM) between different conditions. KAM will be measured during

¹ Note that 24 patients are required for this part of the study (according to the power calculations). However, we will aim to recruit 30 to account for patient drop out between the start and the 6 month follow up.

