| | knee joint centre to the line of action of the ground reaction force in |
| | the frontal plane This in turn has the effect of reducing the moment. |
| 2) Foot | In a study of 14 young healthy subjects, toe in strategy was |
| Progression | successfully used to reduce the KAM, during early stance[13]. Shull |
| Angle – Toe in | et al. (2012) tested the effectiveness of toe-in gait in a group of 12 |
| | subjects with medial KOA and found a significant reduction in the |
| | first peak of the KAM [10]. Similarly in a six week gait re-training |
| | program, Shull et al. (2013) used feedback to encourage increased |
| | toe-in position [41]. After six weeks gait re-training the first peak |
| | KAM was reduced by 20%. Wheeler et al. (2011) healthy subjects |
| | with feedback on KAM and gave suggestions based on previous |
| | studies of how to reduce the KAM. They found that most subjects, |
| | 14/16, opted for a toe-in gait modification [7]. |
| | |
| | Increasing the internal rotation of the foot (toe in) has the effect of |
| | shifting the knee joint centre (KJC) medially and hence closer to the |
| | CoP. This in turn has the effect of reducing the moment arm from the |
| | KJC to the line of action of the force, as with an increase in step |
| | width, which reduces the KAM. It has also been suggested that the |
| | biomechanical reasoning for the reduction in the moment arm is a |
| | shift in the centre of pressure laterally due to an externally rotated |
| | heel [10] This is in agreement with the finding that the KAM is |
| | typically only reduced in the first peak and not throughout stance. |

| 3) Foot | Hunt and Takacs (2014) trained 15 subjects with medial knee OA to |
|----------------|--|
| Progression | walk with a toe-out gait [3] over a ten week gait modification |
| Angle – Toe | program. At the end of the of the program, second stance KAM was |
| out | significantly reduced. Patients also benefited from a reduction in pain |
| | and an improvement in function as indicated by changes in the |
| | Western Ontario and McMaster Universities Osteoarthritis Index |
| | (WOMAC) score. Van den Noort et al. (2013) also reported a |
| | decrease in second peak KAM with an increased toe out position, in |
| | their study of 14 young healthy subjects [13]. However, in this |
| | investigation, the peak KAM in early stance was increased beyond |
| | the normal range. Although first peak KAM was not significantly |

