2. OBJECTIVES

The primary objective of study A is:

• To evaluate the use of real-time visual and audio feedback on the knee adduction moment during gait in patients with knee osteoarthritis to decrease the biomechanical load on the knee via implicit learning and explicit instructions.

The secondary objective of study A is:

- To evaluate changes in the kinematic patterns and electromyographic patterns between baseline (without feedback) and modified (with feedback) gait patterns.
- To identify factors based on the demographic, radiographic and baseline kinematics which increase the likelihood in reducing the KAM using the biofeedback training method.

The primary objectives of study B are:

- To provide proof-of-concept for the use of real-time feedback as a clinical intervention on gait retraining to decrease the biomechanical load on the knee in patients with knee osteoarthritis during a 6 weeks training and 3 and 6 months follow-up.
- To assess changes in pain and function as a result of the biofeedback gait training programme; this will be measured using the WOMAC questionnaire and NRS pain scale. Pain and function are important outcome measures for the patient and are therefore included as additional primary outcome measures.

The secondary objective of study B is:

i) To estimate the reduction in cognitive demand (and hence the extent of motor learning) of the gait modifications over the six week retraining period.

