4.2 Inclusion criteria

Inclusion criteria for the present study (A and B) are knee osteoarthritis on the medial compartment based on the ACR criteria (ACR criteria are age over 50 years, morning stiffness less than 30 minutes, crepitus on active motion, bony tenderness, or absence of palpable warmth of synovium), age between the 50 and 75 years old, Body Mass Index (BMI) between 20 and 30 kg/m2, maximal a score of 7 on the numeric rate scale (NRS) for pain intensity during the past two weeks.

The database of the AMS-OA cohort (Reade) will be screened to identify suitable patients based on the Kellgren-Lawrence (KL) score. This will allow patients with predominantly medial sided osteoarthritis to be identified.

There are several additional inclusion criteria for study B. These include patient satisfaction with the applied gait modification (assessed using the questionnaires in Sections F and G in F1 KneeMo Feedback Questionnaires). In addition, patients should be willing further learn the modifications in training sessions. Finally we require patients to show a clear reduction in the KAM value. Where possible the reduction in KAM (relative to baseline) should be 10%, but this will be at the discretion of the clinicians involved in the decision making process. The

10% KAM reduction is proposed based on previous literature that suggests that this value is attainable through gait retraining and is also clinically relevant in unloading the medial knee joint compartment Shull et al. (2013) and Hunt and Takacs (2014),. Importantly the reduction in knee adduction moment must occur without negative side effects such as a large increase in knee flexion moment or in pain. Furthermore, patients will be included only when there is no clear asymmetry in the change in KAM.

Finally, it is important that patients included in the study are able to walk for 30 minutes independently of a walking frame, crutches or other assistive device (excluding soft braces and orthotics).

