Study B: Based on a significance level alpha = 0.05, power $(1-\beta) = 0.80$, and an anticipated effect size of 0.45 (as above) we require a minimum of 79 participants per group for a between group comparison (i.e. comparison of control and intervention group). This is calculated using a two tailed t-test, assessing the difference between two independent means. Since this is an initial feasibility study, it may not be feasible to recruit such a large number of subjects per group. Therefore we propose that a within group comparison of the baseline to post training may be more suitable. We also anticipate a higher effect size, due to the multiple training sessions. For a within group analysis, using the parameters as specified above and effect size of 0.6, a total of 24 patients are required. This is calculated using a two tailed t-test, assessing the difference between two dependent means (i.e. the differences in the KAM pre and post training) [76;77]. **To account for subject withdrawal we will aim to recruit 30 patients in total.**

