5.1.2 Secondary study parameters/endpoints (if applicable)

The first secondary parameter is the external knee flexion moment (KFM, determined by the GRF and its lever arm in the sagittal plane). The KFM has been shown to play an important role in medial compartment loading and has an interaction with the KAM and internal knee load [13;18;40;78;79]. Pain can cause patients to stiffen the knee during gait, which has a direct influence on the KFM since this alters the lever arm.

Pain is also a secondary study parameter (as measured with the NRS scale), particularly in study B, where it will be assessed on a weekly basis (i.e. at each training session). Patient reported outcome measures are becoming increasingly important in experimental studies such as the proposed study. Therefore, the WOMAC questionnaire will be used to assess changes in pain, function and stiffness of the knee. Patients will be asked to complete this questionnaire five times 1) during Study A and then where applicable to the individual patient 2 and 3) at the start and end of the training phase in Study B 4) at the three month follow up and 5) at the six month follow up.

The amount of muscle co-contraction is also a secondary study parameter, measured with electromyography (EMG) (medial muscles: vastus medialis, medial hamstrings, medial

gastrocnemius; lateral muscles: vastus lateralis, lateral hamstrings, lateral gastrocnemius; and the rectus femoris). Co-contraction will influence the load on the knee [21;27;80-82].

Finally, the kinematic strategies (i.e. joint angles and temporal-spatial parameters like gait velocity, step width and step length) that patients use to decrease the KAM are secondary study parameters.

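### Section 7.1 makes four KAM parameters primary and designates none, pain and function are labelled both primary and secondary, and the powered Study B contrast is not pinned to a walking condition

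*Protocol*

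**What the plan says.** **The outcome.** The Summary states: "Primary outcome measures are change in external knee adduction moment (KAM) between different conditions". Section 5.1.1 likewise gives KAM as the main parameter. Section 7.1 then states: "Four outcomes parameters will be extracted from the gait cycle, i.e. the KAM peaks at early and late stance with the corresponding KFM values", followed by the mid-stance value and the impulse. That makes four KAM parameters with no order among them. The same section sets a single significance threshold of 0.05.

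**Study B entry.** Section 4.2 says: "Finally we require patients to show a clear reduction in the KAM value", with 10% relative to baseline as the target where possible. It does not say which KAM parameter is meant.

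**Pain and function.** Section 2 says of Study B: "Pain and function are important outcome measures for the patient and are therefore included as additional primary outcome measures". Section 7.1 analyses WOMAC and NRS under the primary heading. Section 5.1.2 says: "Pain is also a secondary study parameter (as measured with the NRS scale), particularly in study B", and lists WOMAC there too. The Summary and 7.2 also place NRS pain among the secondary measures.

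**Study B contrast.** Section 4.4 bases n=24 on a two-tailed paired test of "the differences in the KAM pre and post training". Section 7.1 says that "in Study B the change over time will be calculated for both baseline and replication of learned pattern". Section 5.1.1 adds evaluations at 3 and 6 months.

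**The concern.** A power calculation belongs to one variable and one contrast. Here the calculation is for a single paired difference in KAM, while the analysis has four KAM parameters and, in Study B, two walking conditions and several time points, none marked as the one that counts.

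The choice of parameter can change the answer. On toe-out, Table 1 cites a healthy-subject study with a "decrease in second peak KAM with an increased toe out position" and a raised early peak in the same study. On toe-in, it says that the reduction is usually confined to the first peak. Strategies are individualised, so a patient could respond on one peak and not on the other, and could enter Study B on one peak and be tested on another. An analysis plan written after enrolment cannot undo an ambiguity in who was enrolled.

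The conflicting labels have a similar effect: a pain or function result could be reported as primary or as secondary, with protocol text to support either.

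**Working it through.** **1. Reproducing the sample sizes.** Inputs from section 4.4: two-tailed paired t-test, alpha 0.05, power 0.80, effect size d = 0.45 (A) and 0.6 (B). Power is the probability that a noncentral t variable with n−1 degrees of freedom and noncentrality d√n falls outside ±t(1−α/2, n−1).

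- Study A: n = 41, d√n = 0.45 × √41 = 2.88, power 0.803. The smallest n reaching 0.80 is 41, as stated.
- Study B: n = 24, d√n = 0.6 × √24 = 2.94, power 0.804. The smallest n is 24, as stated. Recruiting 30 allows for 20% withdrawal (24/0.8 = 30).

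Both figures are right, each for one variable and one contrast at 0.05.

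**2. False-positive rate if any one of the four parameters may count.** Independent tests: 1 − 0.95⁴ = 0.185. The protocol gives no correlations, so the others are assumed. The results below are simulated for paired t-tests with equal correlation between parameters:

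| Assumed correlation | n = 41 | n = 24 |
|---|---|---|
| 0.5 | 15.6% | 15.5% |
| 0.7 | 13.1% | 13.4% |
| 0.9 | 9.8% | 9.4% |

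**3. Power if that rate were controlled by Bonferroni.** Alpha per parameter is 0.05/4 = 0.0125. Power for any given parameter:

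| Study | n | Power at 0.05 | Power at 0.0125 | n for 0.80 at 0.0125 |
|---|---|---|---|---|
| A (d = 0.45) | 41 | 0.80 | 0.61 | 59 |
| B (d = 0.6) | 24 | 0.80 | 0.60 | 35 |
| B (d = 0.6) | 30 | 0.89 | 0.73 | 35 |

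Bonferroni is conservative when the parameters are correlated, so this is the cautious end.

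**4. Which KAM the sample size refers to.** The three sources in section 4.4 do not use the same parameter: the healthy-subject study uses early stance (2.17 to 1.08), the six-week study the first peak (3.11 to 2.61), and the ten-week study the second peak (2.87 to 2.57). The calculation therefore does not identify the primary variable either.

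**5. Status of pain and function, side by side.**

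| Place | NRS pain | WOMAC pain and function |
|---|---|---|
| Section 2 | primary (B) | primary (B) |
| Section 7.1 | under primary | under primary |
| Section 5.1.2 | secondary | secondary |
| Summary | secondary | not listed |
| Section 7.2 | secondary | not listed |

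**6. Study B contrast.** Section 4.4 compares KAM before and after training but does not say whether the patient walks naturally at both times, uses the learned pattern at both, or natural gait before and learned gait after. Section 7.1 follows natural gait and the learned pattern over time, and designates neither condition and no time point.

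**The case against.** The best defence is that this is early-phase work. The introduction describes Study B as small-scale and exploratory, section 4.4 calls it a feasibility study, and no success criterion is stated. A statistical analysis plan, not shown here, could add a hierarchy or an adjustment. This has weight: the false-positive rate is a consequence of the wording, not a declared decision rule. But the protocol does power both studies at 80%, sets a threshold, and uses an unspecified KAM at the entry step, so the main point stands.

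The evidence for divergence is also limited. It concerns the two peaks only, and the rise in the early peak comes from 14 healthy subjects. In the ten-week patient study the first peak tended to fall with toe-out, and another healthy-subject study found a lower impulse. A reader might infer that all four parameters can move in opposite directions; the protocol does not say so.

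Three further inferences are tempting but unsupported.

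- That 7.1 leaves out the powered Study B contrast. Before and after training can mean natural gait at M1 and M2, which 7.1 covers, and the Summary also lists comparisons between conditions for Study B. The fault is lack of designation, not omission.
- That the learned-pattern trend in Study B has a specific, much lower power because entrants already show a reduction. The documents give neither the share of the effect present at M1 nor the variability of the later change.
- That the error rate in Study A should be counted over every parameter in every modified walking trial. Section 7.1 specifies a linear mixed model and repeated-measures analysis of variance, not a set of separate tests.

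**Conclusion.** The point holds as a defect of specification that should be corrected. Four KAM parameters share primary status, the sample sizes fit only one, and the entry rule and sample-size sources do not show which one. The cost is a false-positive rate of 18.5% under independence, falling to 9 to 10% at correlation 0.9, if any one result may count. With Bonferroni control, power at the planned sizes is instead about 0.6. These figures rest on assumed correlations, on the protocol's own effect sizes applying to every parameter, and on the absence of any stated hierarchy. If all four had to succeed, error would not inflate, but joint power could not exceed that of the weakest parameter.

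The conflict over pain and function is plain on the page and needs no assumption. For function it lies between section 2 with 7.1 and section 5.1.2; a reader might extend it to the Summary and 7.2, but those name only NRS pain. The Study B contrast is ambiguous rather than wrong.

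**What to change.** - In 5.1.1 and 7.1, name one primary KAM variable and make the other three secondary.
- In 4.2, state which KAM variable the required reduction refers to, so that the entry rule is reconciled with the primary variable.
- For each study, designate the one contrast that the sample size refers to and make the rest secondary. For Study A, choose it with the objective in section 2 in view, which covers both implicit learning and explicit instruction. For Study B, state the walking condition and the time points. In that choice, note that comparing the learned pattern after training with natural gait before it would be favoured by enrolling patients who had already shown a reduction, so it would not isolate the effect of training.
- Give WOMAC and NRS pain one status in the Summary and in sections 2, 5.1.2, 7.1 and 7.2.

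The cost is wording only. With one variable and one contrast per study, 41 and 24 (30 recruited) stand as calculated. The downside is that fewer results can be called primary. Keeping four alternative primaries under Bonferroni would instead need 59 and 35 patients before any allowance for withdrawal.

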7.2 Secondary study parameter(s)

The secondary outcome measures, external knee flexion moment (KFM), kinematic strategies (i.e. angles of foot, ankle, knee, hip, pelvis and trunk and temporal-spatial parameters) that patients use to decrease the KAM and pain (NRS scale) will also be assessed using a linear mixed model and repeated measure analysis of variance. Linear mixed model will also be used to determine the change of muscle co-contraction, measured with electromyography (EMG) between the different conditions, the adherence, and satisfaction with the program.

